3.1.2 Pathophysiology of Hepatic Encephalopathy

Hepatic encephalopathy (HE) is a major complication of cirrhosis and the result of a cascade of events that begins with hepatocyte death. Hepatocyte death results in inflammation and fibrosis of the hepatic architecture.

Hepatic encephalopathy (HE) is a reversible neuropsychiatric abnormality that presents in 30% to 45% of patients with cirrhosis and in 10% to 50% of patients with a transjugular intrahepatic portosystemic shunt (TIPS) ([Poordad 2007](#), [Amodio 2001](#), [Guevara 2009](#)). Alterations in the production, metabolism, and excretion of nitrogenous compounds, including ammonia, contribute to the pathogenesis of HE. Ammonia is a by-product of nitrogen metabolism. Approximately half of the body's ammonia is produced in the portal-drained viscera, and half is produced in the colon.

Ammonia is primarily metabolized in the liver to urea and excreted in the urine. In patients with liver disease, this function is diminished or lost, and the skeletal muscle becomes a major elimination pathway. Cirrhotic patients are often muscle wasted, and this can lead to toxic accumulation of ammonia. Metabolism of ammonia in astrocytes in the brain can have both excitatory and inhibitory effects on neurotransmission and causes the common clinical signs of HE including confusion, coma, asterixis, loss of fine motor skills, hyperreflexia, and slow, monotonous speech. Other gut-derived neurotoxins, including mercaptans, phenols, manganese, short chain fatty acids, and bilirubin have also been implicated in the pathogenesis of HE. Precipitating factors for HE include gastrointestinal (GI) bleeding, dehydration, excess dietary protein intake, hypokalemic alkalosis, infection, and constipation. Central benzodiazepine receptors also appear to be upregulated in the presence of ammonia, making patients with cirrhosis more sensitive to the effects of benzodiazepines ([Schiano 2010](#)).

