6.7 Methods of Assigning Subjects to Treatment Groups

This is a double-blind study, in which the identity of the study drug will be unknown to both investigator/evaluator and subjects, as well as all individuals closely associated with the study. Subjects will be randomized to 1 of 5 treatment groups in a 1:1:1:1:1 ratio [rifaximin SSD 40 mg IR (QD and BID), rifaximin SSD 80 mg (QD and BID), and placebo BID]. Each screened subject will be assigned a screening number by the investigational center, which will consist of the XX-digit site number (pre-assigned by Sponsor/designee) and the 3-digit chronological order screening number, starting with '001' (e.g., XX-001, XX-002).

The study drug kit will be assigned to the subject based on a randomization code and kits will be dispensed to the subjects by the randomization system at the Day 2 visit.

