- Change from baseline to OHE resolution in vital sign measurements and clinical laboratory values.
- Incidence of infections, such as spontaneous bacterial peritonitis (SBP), urinary tract infection, pneumonia, bacteremia, and cellulitis.

Open-label Safety Follow-up Phase:

- Reoccurrence of OHE during the 30 day follow-up period.
- Readmission to hospital during the 30 day follow-up period.
- Change from Baseline to study exit in indices of Health Outcome using the Caregiver Burden Inventory (CBI; [Appendix C](#))
- Change during Follow-up Phase (from first follow-up visit post OHE resolution to study exit) in Chronic Liver Disease Questionnaire (CLDQ; [Appendix D](#)).

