7.5.5 Safety Endpoints Analyses

All safety analyses will be performed for the Safety Population. Each analysis will consist of a summary of data within each treatment group.

Adverse Events:

Adverse events will be coded using the Medical Dictionary for Regulatory Affairs (MedDRA) coding dictionary. Treatment-emergent AEs will be defined as any event with a start date occurring on or after initial treatment (baseline visit) or, if pre-existing, worsening after initial treatment (baseline).

The incidence of treatment-emergent AEs will be summarized for each treatment group by body system and MedDRA preferred term. If a subject reports the same AE more than once, then that subject will only be counted once for the summary of that AE, using the most severe intensity.

Treatment-emergent AEs will be summarized as follows:

- Number and percentage of subjects experiencing TEAEs;
- Number and percentage of TEAEs by relationship to study treatment (i.e. related or unrelated);
- Number and percentage of TEAEs by severity (i.e., mild, moderate or severe);
- Number and percentage of subjects experiencing serious AEs (SAEs);
- Number and percentage of subjects experiencing study drug-related SAEs;
- TEAE leading to permanent treatment discontinuation;
- TEAEs with an outcome of death.

The incidence of treatment-emergent AEs of infections, such as SBP, UTI, pneumonia, bacteremia and cellulitis will be summarized by each treatment group.

If a subject reports the same AE more than once, then that subject will only be counted once for the summary of that AE, using the most severe intensity. Severity and AE leading to early termination will also be presented for these infection AEs.

All SAEs and AEs leading to premature withdrawal from the study, and all deaths, will be listed.

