8.1.1 Day 1: Screening / Baseline

The following procedures are to be completed at the Screening/Baseline visit, prior to randomization:

- Informed consent is to be signed by the subject's caregiver prior to performing any study evaluations or procedures, including discontinuing any prohibited medications.
- Allocate subject screening identification number to eligible subjects in ascending order using the next available consecutive number on the list.
- Review Inclusion/Exclusion criteria to ensure subject qualifies for the study.
- Conduct serum pregnancy test (for female subjects of childbearing potential) and confirm that it is negative. Note: Serum pregnancy tests performed upon hospital admission, prior to study consent, may be used at Screening.
- Complete a full physical examination, including evaluation for complications of liver cirrhosis.
- Collect demographic information, significant medical history, and hospital admission data including diagnosis of liver cirrhosis and OHE and HEGI grade.
- Collect vital sign measurements (include weight, height, supine blood pressure, heart rate, respiration rate and temperature). Height will only be collected at Screening.
- Record all concomitant medications administered within the 30 days prior to screening visit, and ensure that all prohibited medications are discontinued
- Collect blood and urine for clinical laboratory tests (hematology, blood chemistry, and urinalysis). Labs drawn within 24 hours of consent may be used at Screening provided all protocol required labs are present.
- Subject must have a Grade 2 or Grade 3 HEGI score ([Appendix A](#)) following lactulose treatment and adequate hydration (IV fluids at PI discretion). NOTE: Duration of hospital admission prior to enrollment is not restricted provided the hydration and lactulose treatment occurred within a reasonable timeframe to subject randomization.
- Determine and record WHC score. ([Appendix B](#))
- Assess Caregiver Burden Index ([CBI; Appendix C](#)).

After all Screening/Baseline procedures have been completed and necessary information has been collected:

- Randomize subject onto study using a randomization code obtained from the IRT.
- Record date, time(s) and dose(s) of lactulose.
- Record all AEs.

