9.1 Operating Definitions for Assessing Safety

9.1.1 Adverse Event

An AE is any untoward medical occurrence in a subject or clinical investigation subject administered a study product and which does not necessarily have a causal relationship with the treatment.

An AE can therefore be any unfavorable and unintended sign (that could include a clinically significant abnormal laboratory finding), symptom, or disease temporally associated with the use of a study product, without any judgment about causality (i.e., whether or not considered related to the study product).

An AE **does** include the following:

- Exacerbation or worsening of a pre-existing illness.
NOTE: if the pre-existing illness is the disease under study, then “exacerbation” refers to an unexpected worsening from the condition at baseline.
- Increase in frequency or intensity of a pre-existing episodic event or condition.
- Condition detected or diagnosed after study product administration even though it may have been present prior to the start of the study.
- Symptom associated with disease not previously reported by the subject.

An AE **does not** include the following:

- Medical or surgical procedures (e.g., surgery, endoscopy, tooth extraction, transfusion) as event terms; the condition that led to the procedure is the AE if it meets the definition of an AE.
- Situations where an untoward medical occurrence has not occurred (e.g., hospitalization for cosmetic elective surgery; and social and/or convenience admissions).

- Overdose of either study product or concurrent medication without any signs or symptoms.
- Symptoms associated with disease, which are consistent with the subject's usual clinical course; unless the subject experiences worsening of their symptom(s) or the symptom(s) meet the criteria for an SAE.

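### Section 7.5.5 ties the treatment-emergent window to the Day 1 baseline visit although study drug starts from Day 2, so pre-dose events, including some infections, may be counted as treatment-emergent

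*Combined protocol and SAP*

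**What the plan says.** Section 7.5.5 defines a treatment-emergent adverse event (TEAE) as "any event with a start date occurring on or after initial treatment (baseline visit", or, for conditions already there, "if pre-existing, worsening after initial treatment (baseline". The infection summary inherits that definition: "The incidence of treatment-emergent AEs of infections, such as SBP, UTI, pneumonia, bacteremia and cellulitis will be summarized by each treatment group". It serves a named safety endpoint in Section 7.1: "Incidence of infections, such as spontaneous bacterial peritonitis (SBP), urinary tract infection, pneumonia, bacteremia, and cellulitis".

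The schedule separates the baseline visit from treatment. Section 8.1.1 (Day 1) states: "The following procedures are to be completed at the Screening/Baseline visit, prior to randomization". Section 6.7 says that "kits will be dispensed to the subjects by the randomization system at the Day 2 visit". Table 1 marks the first-dose row only in the Day 2 to Day 15 column, and Section 8.1.2, not 8.1.1, lists the dosing step.

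Adverse events are collected from informed consent (Sections 9.3.1 and 9.4), and Section 8.1.1 has them recorded on Day 1. Section 9.1.1 includes among adverse events a "Condition detected or diagnosed after study product administration even though it may have been present prior to the start of the study".

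**The concern.** A treatment-emergent event should be one that could have been affected by study drug, so its clock has to start at the first dose. Here the text equates two moments that the schedule puts on different days. Any adverse event recorded in between would be tabulated as on-treatment, although no study drug had been given.

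Infection is where this matters most. Section 3.1.2 says: "Precipitating factors for HE include gastrointestinal (GI) bleeding, dehydration, excess dietary protein intake, hypokalemic alkalosis, infection, and constipation". Among infections, Section 5.2.1.2 excludes sepsis and known HIV but not, for example, a urinary tract infection or pneumonia. A subject whose oral antibiotic can be changed to a parenteral one may enrol. Some subjects can therefore be expected to enter with an infection that is present or emerging. The Day 1 work-up itself (blood tests, urinalysis, full examination) can bring one to light before the first dose. At stake is whether the infection table describes what happened on study drug or partly what subjects brought with them.

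**Working it through.** The plan gives no figure on this point, so the check is to set the rules side by side.

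| Element | Where | What it fixes |
|---|---|---|
| TEAE clock | 7.5.5 | Initial treatment, glossed as the baseline visit; start *date* only |
| Baseline visit | Table 1, 8.1.1 | Study Day 1, procedures before randomization |
| First study drug | 6.7, Table 1, 8.1.2 | From Day 2 |
| Efficacy baseline | 7.5.4 | Date/time of first dose |
| Laboratory and vital-sign baseline | 7.5.6, 7.5.7 | Pretreatment value nearest the first dose |
| AE collection | 9.3.1, 9.4 | From consent, before the first dose |
| Pre-existing conditions | 7.5.5 | Emergent only if they worsen after initial treatment |
| Late-detected conditions | 9.1.1 | Are adverse events; no start-date rule given |

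Applying these rules to four kinds of infection:

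1. *Known, with a start date before Day 1.* It precedes even the Day 1 clock and counts only if it worsens.
2. *Start date from the baseline visit up to the first dose, for example found in the Day 1 work-up and dated Day 1.* It meets the definition as written, although it precedes study drug.
3. *Start on the dosing date but before the dose.* It also counts, because the rule has no time component.
4. *Present at entry, first diagnosed after dosing.* Section 9.1.1 makes it an adverse event. If its start is entered as onset, it is pre-existing and counts only on worsening. If its start is entered as the diagnosis or result date, it counts. The documents do not say which date applies.

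Kinds 2 and 3 follow from the stated rule; kind 4 depends on an unstated convention.

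*Direction only, on assumed inputs.* The documents give neither the share of subjects infected at entry nor any on-treatment infection rate. Suppose true on-treatment incidence is 20% on placebo and 10% on an active arm, and a share c of each arm has a pre-dose infection wrongly counted. The observed rate is then c + (1 − c) × true rate. For c = 10%, placebo is 0.10 + 0.90 × 0.20 = 28.0% and active is 0.10 + 0.90 × 0.10 = 19.0%.

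| c (assumed) | Placebo | Active | Difference | Ratio |
|---|---|---|---|---|
| 0 | 20.0% | 10.0% | 10.0 points | 0.50 |
| 5% | 24.0% | 14.5% | 9.5 points | 0.60 |
| 10% | 28.0% | 19.0% | 9.0 points | 0.68 |
| 20% | 36.0% | 28.0% | 8.0 points | 0.78 |
| 30% | 44.0% | 37.0% | 7.0 points | 0.84 |

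The absolute rates rise in both arms, the difference shrinks modestly, and a ratio moves further toward 1. None of these values of c can be read from the documents.

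**The case against.** The operative words in Section 7.5.5 are *initial treatment*. Section 7.5.4 equates baseline with the first dose, Sections 7.5.6 and 7.5.7 take values nearest the first dose, and Section 5.1 starts the blinded treatment period at randomization. A sensible programmer might therefore use the first dose anyway. Even on the Day 1 reading, the added window runs only from the Day 1 visit to a Day 2 dose, in which few infections would begin. This limits the likely size. It does not remove the conflict, because the parenthesis names a visit that the schedule puts before dosing.

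A reader might go further and infer that the infections which brought subjects into hospital are, as a rule, counted as treatment-emergent. The documents do not support that. The pre-existing clause excludes a known infection unless it worsens. Section 9.1.1 defines an adverse event, not a treatment-emergent one, and sets no start date. A specimen taken on Day 1 and entered as a Day 3 event is possible but not prescribed.

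Nor is baseline infection wholly unrecorded. Section 7.5.3 lists contributing factors for HE episodes, and Section 8.1.1 collects medical history, admission data, laboratory tests and recent medication. What is missing is a link from these to the infection table.

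A reader might also infer a quantified dilution of a treatment contrast. Section 7.5.5 plans summaries within each treatment group, with no test or ratio, and the absolute difference moves little in the illustration.

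**Conclusion.** The concern holds in limited form. The TEAE definition contradicts the visit schedule and the first-dose anchor used elsewhere in Section 7.5. Applied as written, it counts events that start between the baseline visit and the first dose. Infections present at entry but diagnosed later *may* also be counted, if sites enter the diagnosis date as the start date. Infections known before Day 1 are not counted unless they worsen.

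The consequence is possible inflation of the descriptive TEAE and infection rates. Its size cannot be estimated from the documents, and the table under the working shows direction on assumed inputs only. The primary and secondary efficacy analyses and the sample size are unaffected. The definition should be corrected before any unblinded safety table is produced, because otherwise the choice of clock and start date is left to programmers and sites.

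**What to change.** In Section 7.5.5:

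- Define treatment-emergent as onset or worsening at or after the date and time of the first dose of blinded study drug, and delete the baseline-visit gloss. Section 8.1.2 already has dosing dates and times recorded.
- Count an event on the dosing date with unknown time as emergent, as the conservative default.
- State that an infection's start date is that of its first sign or diagnostic specimen, not of the result.
- Report infections present before the first dose separately as baseline infections, so that only new or worsened ones enter the treatment-emergent infection summary.

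The cost is a few lines of text, an instruction to sites on start dates, and one extra summary. TEAE counts will be slightly lower. A dedicated specimen-time field, or a sensitivity table limited to later onsets, would be optional.

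### Severity and relatedness of adverse events are worded as percentages of events, with no denominator stated, so the planned list does not give the number of subjects with any severe or any related TEAE

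*Combined protocol and SAP*

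**What the plan says.** The adverse-event list in protocol section 7.5.5 uses two units.

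Three lines count people: "Number and percentage of subjects experiencing TEAEs", "Number and percentage of subjects experiencing serious AEs (SAEs" and "Number and percentage of subjects experiencing study drug-related SAEs". Two lines count events: "Number and percentage of TEAEs by relationship to study treatment (i.e. related or unrelated" and "Number and percentage of TEAEs by severity (i.e., mild, moderate or severe". Neither of these two says what the percentage is a percentage of.

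Ahead of the list, the section describes TEAE incidence by body system and preferred term. It adds that when a subject reports the same AE more than once, "that subject will only be counted once for the summary of that AE, using the most severe intensity". The rule is repeated for the infection events, of which the section also says "Severity and AE leading to early termination will also be presented for these infection AEs". The synopsis carries the same two statements. Section 7.4 defines the Safety Population as everyone who took at least one dose, analysed by treatment received.

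**The concern.** Neighbouring lines in the same list say subjects, so a programmer will naturally take the other two to mean events and divide by the arm's total number of TEAEs. That total is affected by treatment and by how long events are collected. The blinded phase ends at confirmed resolution, at any time up to 14 days. Subjects who resolve then have 30 days of follow-up with AE recording, and the TEAE definition has a start but no end. If resolution differs between arms as planned (76% against 51%, section 7.3), the time over which events accumulate may differ too, in a direction that cannot be known beforehand. Subject percentages are also affected by follow-up time, but their denominator is fixed.

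At stake is whether the severity and relatedness tables describe a subject's risk. A percentage of events falls when an arm has more mild events, even if no fewer subjects have a severe one.

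**Working it through.** The plan states no figure on this point, so there is none to reproduce. The check is a comparison of the text with itself, followed by simple proportions.

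**1. Does the once-per-subject rule settle the unit?**
- It applies when the same AE is reported more than once, and to the summary of that AE. A subject with five different TEAEs would still enter an overall severity line five times.
- It ranks intensity only. No corresponding rule assigns a subject to related or unrelated.
- No rule gives a subject's maximum severity across different AEs.

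The rule therefore supports subject counts for severity within a preferred term and for the infection events. It does not do so for the overall severity line, or for relatedness at all.

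**2. Do other lines supply the missing counts?** Subjects with any TEAE, any SAE and any drug-related SAE are given. Severe (section 9.5) and serious (section 9.1.2) are defined separately, so SAE counts do not stand in for severe TEAEs. Related SAEs are only part of related TEAEs. Subjects with any severe TEAE and subjects with any related TEAE are not in the list.

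**3. Can the ordering of two arms reverse?** Let S be the number of severe TEAEs and T the total number of TEAEs in an arm.
- Percentage of events = S / T.
- Percentage of subjects = subjects with a severe TEAE / n.
- If arm X has more severe events than arm Y, X still shows the lower event percentage when T_X > T_Y × S_X / S_Y.

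Inputs: n = 65 per arm (planned size, section 5.2). The event counts are assumed, because the protocol gives none. Each severe event is assumed to fall in a different subject.
- Arm X: S = 12, T = 120. Events: 12/120 = 10.0%. Subjects: 12/65 = 18.5%.
- Arm Y: S = 8, T = 50. Events: 8/50 = 16.0%. Subjects: 8/65 = 12.3%.
- Threshold for reversal: 50 × 12/8 = 75 TEAEs in X.

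Range, with Y held at 8/50 = 16.0% and X at 12 severe events:
- T = 60: 20.0% (no reversal)
- T = 75: 16.0% (equal)
- T = 100: 12.0% (reversed)
- T = 150: 8.0% (reversed)

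A second assumed pair behaves the same way. 10/100 = 10% against 5/20 = 25% by events becomes 10/65 = 15.4% against 5/65 = 7.7% by subjects. Its threshold is 20 × 10/5 = 40 TEAEs.

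Reversal thus needs the ratio of total TEAEs to exceed the ratio of severe TEAEs: more than 1.5-fold (75/50) in the first pair and more than 2-fold (40/20) in the second. The same algebra holds for related TEAEs.

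**The case against.** The strongest reply is that this is an ambiguity of wording. No denominator is stated, all safety analyses are done on the Safety Population, and a worst-intensity rule makes sense only if subjects are being counted. That stands in part. A reader might infer that the protocol has fixed an event denominator for every severity display; it has not, and for severity within a preferred term and for infections it points towards subjects. A reader might also infer that the rule and the bullets flatly contradict each other. They need not, since the rule may govern the preferred-term tables and the bullets a separate overall display. What the reply does not supply is a unit for the overall severity line or for relatedness.

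The second reply is that little depends on it. Counts are printed beside percentages, and allocation is equal, so 12 severe events against 8 would be visible. Serious events are by subject; SAEs, AEs leading to withdrawal and deaths are also listed. Safety is summarised within arms with no test. Severity and relatedness are not named among the safety endpoints in section 7.1, where TEAE incidence is. All of this is correct and limits the importance of the point. Event counts still do not show how many subjects were affected.

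The third reply is that the reversal rests on invented counts. It does: the arithmetic shows that it is possible and gives no indication of how likely it is.

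**Conclusion.** The point holds as a defect in the unit of two descriptive safety summaries. Followed literally, section 7.5.5 gives percentages of each arm's own event total and leaves out the number of subjects with any severe or any related TEAE. The gap is clearer for relatedness, where no per-subject rule exists, than for severity, where one exists for repeats of the same event.

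In the first illustration, 18.5% against 12.3% of subjects appears as 10.0% against 16.0% of events. This rests on assumed event counts, 65 treated subjects per arm and one severe event per affected subject.

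It would be wrong to infer that the trial's safety conclusions will be reversed, or that any formal comparison is affected. The documents give no event rates, and no test or decision rule uses these percentages. The primary efficacy analysis is untouched. The change is worth making because it is cheap and supplies two counts that the list lacks.

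**What to change.** In protocol section 7.5.5, replace the two bullets with:
- *Number and percentage of subjects with at least one TEAE, by maximum severity.*
- *Number and percentage of subjects with at least one related TEAE.*

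State that the denominator for both is the arm's Safety Population and that maximum severity is taken across all of a subject's TEAEs. The existing rule for repeats of the same AE can stay for the preferred-term tables. Event counts may be kept as an additional column.

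The cost is two lines of protocol wording and slightly changed table shells. No new data are needed, because severity and causality are already assessed for each AE under sections 9.5 and 9.6.
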